10.3 ADDITIONAL EFFICACY PARAMETER

10.4 SUBGROUP ANALYSES

Primary and secondary efficacy variable summaries will be repeated for the following subgroups by study visit using OC data:

- Gender: male and female
- Age groups: ≥ 9 and < 18 years; ≥ 18 years
- Race: white, African-American/Black, other
- Body mass index: $< 25 \text{ kg/m}^2$ and $\geq 25 \text{ kg/m}^2$
- Baseline acne severity (IGA score): moderate and severe
- Hormonal contraceptive use in females: female subjects who use hormonal contraceptives versus female subjects who do not
- Weight groups: 33 to 54 kg, 55 to 84 kg, and 85 to 136 kg

10.5 OTHER EFFICACY PARAMETERS

10.5.1 IGA for Non-facial Sites

10.5.2 Skindex Questionnaire

[REDACTED]	[REDACTED]

[REDACTED]

[REDACTED]

10.6 ADDITIONAL EFFICACY ANALYSES

[REDACTED]

11.0 SAFETY ANALYSES

The safety analysis will be performed using the Safety Population. The safety parameters will include adverse events (AEs) and clinical laboratory, vital sign, ECG, and noninflammatory lesion counts parameters. For each safety parameter of the clinical laboratory, vital sign, ECG parameters, and noninflammatory lesion counts parameters, the last nonmissing safety assessment on or before the date of the first dose of the investigational product will be used as the baseline for all analyses of that safety parameter. Continuous variables will be summarized by number of subjects and mean, SD, median, minimum, and maximum values. Categorical variables will be summarized by number and percentage of subjects.

11.1 ADVERSE EVENTS

Adverse events will be coded by system organ class and preferred term using the *Medical Dictionary for Regulatory Activities*, version 18.0 or newer.

Adverse events with onset on or after the first dose date of the study drug will be considered as “treatment-emergent adverse event (TEAE)”. An AE that occurs more than 30 days after the date of the last dose of the investigational product will not be counted as a TEAE. Adverse events summaries will present the number and percentage of subjects reporting an adverse event by treatment and overall as well as the number of events reported. The denominators for calculating the percentages by treatment will be based on the number of subjects exposed in the Safety population to each treatment and overall. The treatment will be based on the double-blind treatment received. For subjects who are in PK schedule 3, the TEAE summary described will comprise data prior to the active dose taken at the Week 12 visit. Further adverse events experienced after this Week 12 dose will be listed separately for these subjects.

The number and percentage of subjects reporting TEAEs in each treatment group and overall will be tabulated by system organ class and preferred term and further categorized by severity and relationship to study treatment. If more than 1 AE is coded to the same preferred term for the same subject, the subject will be counted only once for that preferred term using the greatest severity and strictest causality for the summarization by severity and relationship.

The incidence of common ($\geq 2\%$ of subjects in any treatment group) TEAEs will be summarized by preferred term and treatment group and will be sorted by decreasing frequency for sarecycline treatment group.

The total number of TEAEs by severity and relationship to study treatment will be summarized by treatment group.

A serious adverse event (SAE) that occurred between the date of the first dose of the investigational product and 30 days after the date of the last dose of the investigational product, inclusive, will be considered an on double-blind therapy SAE. However, for any subject in the PK schedule 3 group, SAEs that occur after the Week 12 active dose will not be included. These events will be listed separately. The number and percentage of subjects who have on-therapy SAEs will be summarized by preferred term and treatment group and will be sorted by decreasing frequency for sarecycline treatment group. In addition, the incidence of on-therapy SAEs that led to death will be summarized separately by preferred term for each treatment group.

The number and percentage of subjects in the Safety Population who have AEs leading to premature discontinuation of the investigational product will be summarized by preferred term and treatment group and will be sorted by decreasing frequency for sarecycline treatment group.

Gastrointestinal AEs of special interest will be pre-specified prior to database lock. The number and percentage of subjects in the Safety Population who have gastrointestinal TEAEs of special interest will be summarized by preferred term and treatment group and will be sorted by decreasing frequency for sarecycline treatment group. In addition, these TEAEs will be further categorized by relationship to study treatment.

For the Screened Population, separate tabular displays will be presented for subjects who died, subjects with SAEs, and subjects with AEs leading to premature discontinuation.

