9.6.2.1 Adverse Events

Adverse events will be assessed from the time of signing the consent/assent form until exit from the study. At every study visit, subjects will be asked a standard question to elicit any medically related changes in their well-being. They will also be asked if they have been hospitalized, had any accidents, used any new medications, or changed any current medication regimens (both prescription and over-the-counter medications).

Definition of Terms

Adverse Event: Any untoward medical occurrence associated with the use of a drug in humans, whether or not considered drug related. In addition to novel events, an adverse event may be an exacerbation of a pre-existing medical condition that was present before the subject was assigned to a treatment group. Each adverse event is described using the following classifications: severity, relatedness, and seriousness.

Severity: An adverse event may present in different severities, as categorized below.

Mild: Noticeable to the subject, does not interfere with the subject's daily activities, and usually does not require additional therapy or dose adjustment.

Moderate: May interfere with the subject's daily activities and may require additional therapy.

Severe: May severely limit the subject's daily activities and typically requires therapy or intervention.

Relatedness: The determination of whether an adverse event is related to treatment is based on information regarding the degree to which the study drug has caused or contributed to the event and will be categorized according to the following criteria:

Not Related: There is no medical evidence to suggest that the AE may be related to study drug usage.

Possibly Related: There is medical evidence to suggest that the AE may be related to study drug usage. However, other medical explanations cannot be excluded as a possible cause.

Related: There is strong medical evidence to suggest that the AE is related to study drug usage.

Serious: An adverse event is considered "serious" if, in the view of either the investigator or Sponsor, it results in any of the following outcomes:

- Death: the adverse event causes or contributes to the death. Death is usually considered to be the outcome of an event; the event that leads to death is defined as the serious adverse event (SAE).

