Assessing and Following: The Investigator is responsible for assessing all adverse events that occur at any time during the study. The Investigator must make a determination of relatedness, seriousness, and severity on the Adverse Events page of the case report form for each adverse event. All adverse events must be followed to adequate resolution or stabilization. If the adverse event has not resolved or stabilized by the time the subject completes the final study visit, the Investigator will follow the status of the subject's adverse event for at least 30 days beyond the subject's final study visit, unless directed otherwise by the Sponsor. If Investigator becomes aware of any SAEs that occurred within 30 days after the subject completed the study, the SAE must be reported to the Sponsor.

Documenting: All adverse events during the study will be documented in the subject's medical record. This information will then be transcribed on the adverse events page of the case report form by designated study personnel. Required information includes a description of the event, date of onset, date of resolution, if death occurred, the action taken to manage the adverse event, as well as relatedness, seriousness, and severity.

Adverse event information must be recorded regardless of its relatedness to the use of the study drug. Adverse events resulting from concurrent illnesses, reactions to concurrent medications, or progression of disease states must also be reported.

Reporting: 1) The investigator is responsible for reporting adverse events to the IRB according to agreements and instructions from that board or committee that oversees this research, as well as according to applicable regulations. 2) Additionally, all adverse events will be reported to the Sponsor on the case report form, and all serious adverse events, whether expected or unexpected, related or unrelated, must be reported to the Sponsor, by telephone or facsimile using the "Serious Adverse Event Report" form provided by the Sponsor, within 24 hours after the Investigator first learns of the event.

Warner Chilcott Clinical Pharmacovigilance:

Phone: [REDACTED] or [REDACTED]

Fax: [REDACTED]

Email: [REDACTED]

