9.6.2.3 Physical Examinations

Physical examinations will be performed at screening (SV1 and SV2, as necessary) and at Visit 4/ET **and Visit 5 (for subjects participating in PK Schedule 3)**. Physical examinations will include an evaluation of the following: body as a whole, skin, head, ears, eyes, nose and throat, cardiovascular, respiratory, musculoskeletal, neurologic, lymphatic/thyroid, abdomen, body weight, and height (screening only).

Clinically significant findings identified during screening will be captured in Medical History. Clinically significant changes from baseline during the study will be captured as an adverse event.

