11.6 Safety Analyses

11.6.1 Adverse Events

Treatment-emergent adverse events will be classified into a standardized terminology using the Medical Dictionary for Regulatory Activities (MedDRA) system organ classifications and preferred terms. Adverse events with onset on or after the first dose date of test or reference article and prior to or on study completion will be considered as “treatment-emergent.”

Although a preferred term or system organ class may be reported more than once for a subject, each subject will only be counted once in the incidence count for that preferred term or system organ class for each particular summary. Summaries of safety data will be generated for the following summary types:

- Overall summaries
- Summaries by MedDRA system organ class, MedDRA preferred term, test or reference article relationship, and severity.
- Summaries by MedDRA preferred term and test or reference article relationship in descending order.
- Summaries of serious adverse events by MedDRA preferred term and test or reference article relationship in descending order.
- Summaries of adverse events by MedDRA system organ class, MedDRA preferred term, and test or reference article relationship for the primary events leading to premature discontinuation from the study.

These summaries will present the number and percentage of subjects reporting an adverse event by treatment and overall as well as the number of events reported. The denominators for calculating the percentages by treatment will be based on the number of subjects exposed in the Safety population to each treatment and overall. The treatment will be based on the **double-blind** treatment received. **For subjects who are in PK Schedule 3, the treatment-emergent adverse event summary described above will comprise data prior to the active dose taken at the Week 12 visit. Further adverse events experienced after this Week 12 dose will be listed separately for these subjects.**

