The study includes a screening period of up to 35 days to establish eligibility and baseline conditions followed by a 12-week treatment period. Eligible subjects will be randomized in a 1:1 ratio to receive daily oral doses of either 1.5 mg/kg sarecycline tablets or placebo tablets. Subjects will return to the clinic on an outpatient basis following 3, 6, 9 and 12 weeks of treatment. At each clinic visit, facial acne will be evaluated through lesion counts and Investigator's Global Assessment (IGA) scores by visual inspection; non-facial inflammatory acne will also be evaluated by IGA of the neck, chest and back. The co-primary efficacy endpoints of the study are the absolute change from baseline in the facial inflammatory lesion count at Week 12 and a dichotomized IGA (dichotomized to reflect either 'success' or 'failure' with 'success' defined as at least a 2-point decrease from baseline in the IGA assessment and a score of clear [0] or almost clear [1] on the IGA assessment) at Week 12. Safety evaluations (adverse events, vital signs, clinical laboratory evaluations, electrocardiograms (ECG) and physical examinations) will be conducted at specific treatment period visits and at study termination.

The study drug, referred to as investigational product in this statistical analysis plan, quantity and dispensing schedule for this study are as follows:

Visit	Quantity Dispensed
Screen Visit (SV) 2	30
1	30
2	30
3	30

The schedule of evaluations for Study SC1401 is presented in Table 4-1.

Table 4–1. Study Schedule of Events: Study SC1401

	Screening Period		Treatment Period					
	SV1	SV2 (Baseline Assessment)	Telephone Contact Week 1 ± 3 d	Visit 1 Week 3 ± 3 d	Visit 2 Week 6 ± 3 d	Visit 3 Week 9 ± 3 d	Visit 4 Week 12 /ET ± 3 d	Visit 5 ^d Week 13 /ET ± 3 d
Informed Consent	X							
Assign Subject Number using the IRT	X							
Inclusion/Exclusion	X	X						
Demographic Data	X							
Medical/Surgical History	X							
Physical Examination	X	X ^a					X	X
Height & Weight	X	Weight only					Weight only	Weight only
Vital Signs	X	X		X	X	X	X	X
Hematology, Serum Chemistry, Urinalysis and Lipids	X	X ^b		X			X	
TSH, Free T4 and T3	X						X	
Urine pregnancy test	X	X		X	X	X	X	X
ECG	X						X	
Facial Investigator's Global Assessment		X		X	X	X	X	
Facial Lesion Counts		X		X	X	X	X	
Facial Photographs		X		X	X	X	X	
Non-facial Investigator's Global Assessment		X		X	X	X	X	

Table 4–1. Study Schedule of Events: Study SC1401

	Screening Period		Treatment Period					

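### The TEAE definition rests on onset date alone, so on-drug worsening of an adverse event that began in screening can be missed, depending on how sites record it

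*SAP*

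**What the plan says.** SAP 11.1 opens its definition with "Adverse events with onset on or after the first dose date of the study drug will be considered as" treatment-emergent. It closes the TEAE window with a second date rule: "An AE that occurs more than 30 days after the date of the last dose of the investigational product will not be counted". For subjects in PK Schedule 3, events after the active dose given at Week 12 are listed separately. Protocol 11.6.1 uses the same starting point: "Adverse events with onset on or after the first dose date of test or reference article and prior to or on study completion" are treatment-emergent. Neither section mentions an increase in severity or seriousness.

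Collection starts well before dosing. Protocol 9.6.2.1 states: "Adverse events will be assessed from the time of signing the consent/assent form until exit from the study". SAP 4.0 gives the length of the pre-dose interval: "The study includes a screening period of up to 35 days to establish eligibility". Protocol 9.5 places washout of excluded therapies in that interval, and Protocol 9.5.1 has adverse events queried or recorded at both screening visits.

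On what counts as an event, Protocol 9.6.2.1 says "an adverse event may be an exacerbation of a pre-existing medical condition that was present before the subject was assigned to a treatment group". Protocol 9.6.2.3, on physical examinations, adds "Clinically significant changes from baseline during the study will be captured as an adverse event". On what is recorded, Protocol 9.6.2.1 says "Required information includes a description of the event, date of onset, date of resolution", followed by items that include relatedness, seriousness and severity. It names no date for a change in severity, and it gives no rule for an event that is already on the form and then gets worse.

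**The concern.** A subject can reach first dose with an adverse event already open. If that event becomes more severe on treatment, the worsening is what a treatment-emergent summary is meant to show. Under an onset-only rule it is counted only if someone has entered it as a new event with a post-dose date. The plan neither requires that entry nor compensates for its absence in the analysis definition.

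Two things are at stake. The first is completeness of the main safety tables. The second is consistency: with about 50 sites and no stated recording rule, the same clinical course could be a TEAE at one site and not at another.

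**Working it through.** The point concerns a definition, and the plan gives no figure to reproduce. The check is to follow one case through the rules as written.

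**Case.** A headache is recorded as mild at SV2 and becomes severe in Week 2, without becoming serious and without stopping treatment.

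- *Route A, new record.* The site treats the worsening as an exacerbation of a pre-existing condition, which Protocol 9.6.2.1 allows, and enters it with a Week 2 onset. Onset is after first dose, so it is a TEAE and is counted as severe.
- *Route B, same record.* The site keeps the SV2 onset date, whether or not it updates the severity. Onset is before first dose, so it is not a TEAE.

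The documents do not choose between the routes.

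**Displays that depend on the choice (SAP 11.1).**

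| Display | Uses the TEAE flag? | Route B event counted? |
|---|---|---|
| TEAEs by system organ class and preferred term | Yes | No |
| TEAEs by severity and by relationship | Yes | No |
| Common TEAEs (at least 2% in any group) | Yes | No |
| Gastrointestinal TEAEs of special interest | Yes | No (if the event were gastrointestinal) |
| On-therapy SAEs | No; based on when the SAE occurred | Only if serious, and if *occurred* is read as the date it became serious |
| Adverse events leading to discontinuation | No; worded for adverse events generally | Only if treatment was stopped |

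The last two rows do not reach the case above, a non-serious event that worsens while the subject stays on treatment.

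**Are pre-dose records expected?** Yes. SAP 16.5 has a rule for missing severity in events that started before first dose: they are set to mild, while events starting on or after first dose are set to severe. SAP 16.6 assigns a missing relationship as related only for events starting on or after first dose. A Route B event therefore also misses these conservative defaults. By contrast, SAP 16.7 moves an ambiguous partial onset date to the first-dose date, which favours inclusion. The lack of a worsening clause does not fit that approach.

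**Size.** The documents give no rate of events open at first dose and no rate of worsening. As an assumption only, suppose 3% to 10% of 1000 subjects have an open event and 10% to 20% of those worsen:

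- Low: 1000 × 0.03 × 0.10 = 3 subjects.
- High: 1000 × 0.10 × 0.20 = 20 subjects.
- Split evenly between arms: 1.5 to 10 per arm, over all preferred terms together.

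**The case against.** The strongest reply is that the protocol already supplies a route. An exacerbation of a condition present before randomization may be an adverse event in its own right, and clinically significant changes from baseline are captured as events. A site following those sentences would enter the worsening with a post-dose onset and it would be counted. This stands to the extent that exclusion is not certain. It does not close the gap. The first sentence says what may be an event, without saying how to record worsening of one already on the form. The second sits under physical examinations and does not clearly reach symptoms such as headache or nausea.

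Four stronger readings are tempting, and the documents do not support them:

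- *That every worsening event is lost from every treatment-emergent table.* This would need all sites to follow Route B. The adverse event page and its completion guideline are not among the documents, and the protocol's list of required information is not stated to be exhaustive.
- *That the most serious cases are lost too.* On-therapy SAEs and discontinuation events do not use the TEAE flag. SAP 11.1 also displays deaths, SAEs and discontinuation events for the Screened Population.
- *That the loss is large against the 2% threshold for common TEAEs.* That threshold, 0.02 × 500 = 10 subjects, applies to one arm and one preferred term. The assumed 3 to 20 subjects cover both arms and all terms, so the two cannot be compared.
- *That the safety comparison is necessarily pulled toward no difference.* Events also worsen on placebo. The difference shrinks only to the extent that the worsening is caused by the drug, and the documents say nothing on that.

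**Conclusion.** The point holds as a gap in the specification. Both TEAE definitions use onset date only, neither has a worsening clause, and the recording of worsening in a screening-onset event is not stated. Where such an event keeps its original onset date, its on-drug worsening is omitted from the TEAE, severity, relatedness, common-TEAE and gastrointestinal special-interest tables. The two displays that do not use the flag protect only part of the range.

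The number affected cannot be derived from the documents, and the illustrative range above should not be quoted as an estimate. The conclusion rests on the definitions as written and on the fact that pre-dose events are collected. It assumes nothing about how often sites kept the original date. The change is worth making because it removes the dependence on site practice at little cost.

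**What to change.** In SAP 11.1, and in Protocol 11.6.1 if that document is amended, define a TEAE as either:

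1. an adverse event with onset on or after first dose; or
2. an adverse event present before first dose that increases in severity or becomes serious on or after first dose.

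Keep the SAP's existing limits and apply them to the date of worsening. Worsening more than 30 days after the last dose is not counted, and for PK Schedule 3 subjects worsening after the Week 12 active dose goes to the separate listing.

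A new instruction to sites would come too late, since SAP 17.0 records that Amendment 1 was written after all patients had completed and before database lock. The SAP clause can still be applied. Before unblinding, list all adverse events open at first dose and identify increases in severity or seriousness from the eCRF audit trail described in Protocol 12.2. The audit trail shows when an entry was changed, which may not be when the event worsened, so use a query where the date is unclear or the record shows no change.

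Cost: one sentence in the SAP, a small blinded data review with some queries, and slightly higher TEAE counts.

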11.2 CLINICAL LABORATORY PARAMETERS

Descriptive statistics for clinical laboratory values (in SI units) and changes from the baseline values at each assessment time point will be presented by double-blind treatment group for the following laboratory analytes:

Hematology: Hemoglobin, hematocrit, red blood cell count, mean cell volume, white blood cell count, white blood cell count differential, and platelet count

Chemistry: albumin, alanine aminotransferase, aspartate aminotransferase, blood urea nitrogen, gamma glutamyl transferase, glucose, lactate, dehydrogenase, total bilirubin, creatine phosphokinase, total protein, serum creatinine, sodium potassium, calcium, chloride, bicarbonate, and phosphorus

Urinalysis: color, specific gravity, potential for hydrogen (pH), leukocytes, ketones, protein, glucose, blood, and bilirubin

Lipid Profile: total cholesterol and triglycerides

Thyroid Function: thyroid stimulating hormone and free T4 and T3

Other Urine pregnancy test

Continuous clinical laboratory analytes will be summarized by double-blind treatment, analyte, and visit using descriptive statistics. Categorical laboratory analytes, classified as normal or abnormal (low or high), will be summarized by double-blind treatment group,

Clinical laboratory test values will be considered potentially clinically significant (PCS) if they meet either the lower-limit or higher-limit criteria provided by the [REDACTED]

[REDACTED] (Appendix 1). The number and percentage of subjects who have PCS postbaseline clinical laboratory values will be tabulated by double-blind treatment group for the treatment period. The percentages will be calculated relative to the number of subjects with available non-PCS baseline values and at least 1 postbaseline assessment for the treatment period. The numerator will be the total number of subjects with available non-PCS baseline values and at least 1 PCS postbaseline value for the treatment period. A supportive tabular display of subjects with PCS postbaseline values will be provided, including SID, study center number, and baseline and all postbaseline (including non-PCS) values.

In addition, a tabular display showing all AEs that occurred in subjects who had PCS postbaseline clinical laboratory values will be provided.

Shift tables from baseline to end of the double-blind study period for clinical laboratory parameters will be presented by treatment group for the following categories: low, normal, and high.

Subjects with potential drug induced liver injury (elevated AST or ALT 3 times upper limit of normal (ULN) or greater and elevated bilirubin greater than 2 times ULN) will be listed. In addition, a tabular display showing all AEs that occurred in subjects with potential drug induced liver injury will be provided.

